8.1.6 Storage and Stability

PD 0332991 capsules should be stored at controlled room temperature (15-25°C, 59-77°F) in their original container. PD 0332991 oral solution should be stored in its original container and in accordance with the conditions described in the oral solution IPM. Medication should be kept in a secured locked area at the study site in accordance with applicable regulatory requirements. Returned medication should be stored separately from medication that needs to be dispensed.

To ensure adequate records, PD 0332991 capsules and oral solution will be accounted for as instructed by Pfizer. Unless otherwise authorized by Pfizer, at the end of the clinical trial all drug supplies unallocated or unused by the subjects must be returned to Pfizer or its designee. All containers of PD 0332991 that were sent to the investigator throughout the study must be returned to the sponsor or designee, whether they are used or unused, and whether they are empty or contain capsules/solution.

8.1.7 Administration

Patients should be encouraged to take their dose of PD 0332991 at approximately the same time each day. Patients should be instructed to record daily administration of the study drugs in a patient diary.

Patients must be instructed to withhold their daily dose of PD 0332991 on pharmacokinetic sampling days until the pre-dose pharmacokinetic sample and safety assessments (ie, hematology, blood chemistry and ECGs) have been completed. On days the patient is in the clinic, PD 0332991 will be taken when instructed by the investigator.

Patients who miss a day's dose must be instructed NOT to "make it up" the next day. Patients who vomit any time after taking a dose must be instructed NOT to "make it up," and to resume treatment the next day as prescribed. Patients who inadvertently take 1 extra dose during a day must be instructed to skip the next day's dose

PD 0332991 Capsules

Patients should be instructed to swallow PD 0332991 capsules whole and not to chew them prior to swallowing. No capsule should be ingested if it is broken, cracked, or otherwise not intact. PD 0332991 capsules will be administered once a day, orally, for 21 days followed by 7 days off treatment in 28-day cycles. **Patients should take PD 0332991 with food.**

PD 0332991 Oral Solution

For patients who are unable to swallow capsules, a PD 0332991 oral solution is available as of IRB/EC approval of Amendment 5.

For patients who develop inability to swallow capsules during the study, it is allowed to switch to the PD 0332991 oral solution.

The PD 0332991 oral solution (25 mg/mL) will be administered using an oral syringe at volumes corresponding to the dose prescribed by the investigator (125 mg dose = 5mL, 100 mg dose = 4 mL, and 75 gm dose = 3 mL). Detailed instructions for administration of the oral solution can be found in the DAI.

PD 0332991 oral solution will be administered once a day, orally or via feeding tube, for 21 days followed by 7 days off treatment in 28-day cycles. The route of administration of the oral solution (oral vs via feeding tube) will be recorded in patient's dosing diary and the study CRF.

Patients can take PD 0332991 oral solution with or without food.

8.1.8 Special Handling Instructions

Females of childbearing potential should not handle or administer the study agent unless they are wearing gloves.

8.1.9 Pregnancy

The nonclinical safety profile of palbociclib has been well characterized through the conduct of single- and repeat-dose toxicity studies up to 39 weeks in duration, and safety pharmacology, genetic toxicity, reproductive and developmental toxicity, and phototoxicity studies. Consistent with the pharmacologic activity of palbociclib (cell cycle inhibition, CDK4/6 inhibition), the primary target organ findings included hematolymphopoietic (decreased cellularity of bone marrow and lymphoid organs) and male reproductive organ (seminiferous tubule degeneration, and secondary effects on the epididymis, prostate, and seminal vesicle) effects in rats and dogs, and altered glucose metabolism that was accompanied by effects on the pancreas and secondary changes in the eye, teeth, kidney, and adipose tissue in rats only, and effects on bone in rats only that were observed following single and/or repeat dosing at clinically relevant exposures. Altered glucose metabolism (hyperglycemia/glucosuria) correlated with pancreatic islet cell vacuolation that was determined to reflect a loss of beta cells with corresponding decreases in insulin and C-peptide. The reversibility of the effects on glucose homeostasis, pancreas, eye, kidney, and bone was not established following a 12-week non-dosing period; whereas partial to full reversal of effects on the hematolymphopoietic and male reproductive systems, teeth, and adipose tissue were observed. Additionally, a potential for QTc prolongation and hemodynamic effects were identified from safety pharmacology studies, and developmental toxicity was identified from embryo-fetal development studies in the rat and rabbit. Though gastrointestinal effects would be anticipated from a cell cycle inhibitor and while effects were observed in rats and dogs following single- and repeat-dose studies up to 3 weeks in duration (emesis, fecal changes, and microscopic changes in stomach and intestines), the effects were of limited severity at clinically relevant doses. Gastrointestinal effects were not prominent in longer duration studies, limited to effects on the glandular stomach and rodent-specific effects on the non-glandular stomach in rats following 27 weeks of intermittent dosing that did not reverse during a 12-week non-dosing period. Additional palbociclib-related findings considered non-adverse at tolerated doses based on limited severity and/or absence of degenerative changes included cellular vacuolation in multiple tissues that was morphologically consistent with phospholipidosis; hepatic (increases in liver enzymes, hepatocellular hypertrophy/increased vacuolation), renal (increased CPN), adrenal (cortical cell hypertrophy), and respiratory (clinical signs, tracheal epithelial cell atrophy) effects; and prolonged coagulation times. Reversibility (partial or full) was established for these additional toxicities. Finally, palbociclib was determined to be an aneugen, for which a no effect exposure was identified

8.2 Cetuximab (Erbix)

8.2.1 Cetuximab Description

Cetuximab is an anti-EGFR human-to-murine chimeric antibody.

8.2.2 Clinical Pharmacology

The epidermal growth factor receptor (EGFR, HER1, c-ErbB-1) is a transmembrane glycoprotein that is a member of a subfamily of type I receptor tyrosine kinases including EGFR, HER2, HER3, and HER4. The EGFR is constitutively expressed in many normal epithelial tissues, including the skin and hair follicle. Expression of EGFR is also detected in many human cancers including those of the head and neck, colon, and rectum.

Cetuximab binds specifically to the EGFR on both normal and tumor cells, and competitively inhibits the binding of epidermal growth factor (EGF) and other ligands, such as transforming growth factor-alpha. *In vitro* assays and *in vivo* animal studies have shown that binding of cetuximab to the EGFR blocks phosphorylation and activation of receptor-associated kinases, resulting in inhibition of cell growth, induction of apoptosis, and decreased matrix metalloproteinase and vascular endothelial growth factor production. Signal transduction through the EGFR results in activation of wild-type KRAS protein.

However, in cells with activating *KRAS* somatic mutations, the mutant *KRAS* protein is continuously active and appears independent of EGFR regulation.

In vitro, cetuximab can mediate antibody-dependent cellular cytotoxicity (ADCC) against certain human tumor types. *In vitro* assays and *in vivo* animal studies have shown that cetuximab inhibits the growth and survival of tumor cells that express the EGFR. No antitumor effects of cetuximab were observed in human tumor xenografts lacking EGFR expression. The addition of cetuximab to radiation therapy or irinotecan in human tumor xenograft models in mice resulted in an increase in anti-tumor effects compared to radiation therapy or chemotherapy alone.

8.2.3 Pharmacokinetics and Drug Metabolism

Cetuximab administered as monotherapy or in combination with concomitant chemotherapy or radiation therapy exhibits nonlinear pharmacokinetics. The area under the concentration time curve (AUC) increased in a greater than dose proportional manner while clearance of cetuximab decreased from 0.08 to 0.02 L/h/m² as the dose increased from 20 to 200 mg/m², and at doses >200 mg/m², it appeared to plateau. The volume of the distribution for cetuximab appeared to be independent of dose and approximated the vascular space of 2–3 L/m².

Following the recommended dose regimen (400 mg/m² initial dose; 250 mg/m² weekly dose), concentrations of cetuximab reached steady-state levels by the third weekly infusion with mean peak and trough concentrations across studies ranging from 168 to 235 and 41 to 85 µg/mL, respectively. The mean half-life of cetuximab was approximately 112 hours (range 63–230 hours). The pharmacokinetics of cetuximab were similar in patients with HNSCC and those with colorectal cancer. Based on a population pharmacokinetic analysis, female patients with colorectal cancer had a 25% lower intrinsic clearance of cetuximab than male patients. Qualitatively similar, but smaller gender differences in cetuximab clearance were observed in patients with HNSCC. The gender differences in clearance do not necessitate any alteration of dosing because of a similar safety profile.

8.2.4 Supplier

Cetuximab is commercially available and is listed in the compendia as indicated for the therapy of HNSCC.

8.2.5 Dosage Form

Each single-use, ready to use 50-mL vial contains 100 mg of cetuximab at a concentration of 2 mg/mL and is formulated in a preservative-free solution containing 8.48 mg/mL sodium chloride, 1.88 mg/mL sodium phosphate dibasic heptahydrate, 0.42mg/mL sodium phosphate monobasic monohydrate, and Water for injection, USP.

8.2.6 Storage and Stability

Cetuximab should be stored in a secure area according to local regulations. Store vials under refrigeration at 2° C to 8° C (36° F to 46° F). DO NOT FREEZE. Increased particulate formation may occur at temperatures at or below 0°C. This product contains no preservatives. Preparations of cetuximab in infusion containers are chemically and physically stable for up to 12 hours at 2° C to 8° C (36° F to 46° F) or up to 8 hours at controlled room temperature (20° C to 25° C; 68° F to 77° F). Discard any remaining solution in the infusion container after 8 hours at controlled room temperature or after 12 hours at 2° to 8° C. Discard any unused portion of the vial.

8.2.7 Safety Precautions

Appropriate mask, protective clothing, eye protection, gloves, and Class II vertical-laminar-airflow safety cabinets are recommended during preparation and handling. Opened vials must be disposed of at the investigational center as chemotherapy or biohazardous waste provided documented procedures for destruction are in place.

Cetuximab therapy should be used with caution in patients with known hypersensitivity to cetuximab, murine proteins, or any component of this product. It is recommended that patients wear sunscreen and hats and limit sun exposure while receiving cetuximab as sunlight can exacerbate any skin reactions that may occur.

8.2.8 Premedication

In an effort to prevent a hypersensitivity reaction, all patients should be premedicated with diphenhydramine hydrochloride 50 mg (or an equivalent antihistamine) IVPB given at least 30 minutes prior to the cetuximab. Premedication will also include 1 Liter normal saline, hydrocortisone 100 mg IVPB and albuterol inhalation (by nebulizer or inhaler) according to standard of care procedures.

8.2.9 Preparation and Administration

Cetuximab must not be administered as an IV push or bolus. Cetuximab must be administered with the use of a low protein binding 0.22-micrometer in-line filter. Cetuximab is supplied as a 50-mL, single-use vial containing 100 mg of cetuximab at a concentration of 2 mg/mL in phosphate buffered saline. DO NOT SHAKE OR DILUTE.

Cetuximab can be administered via infusion pump.

Infusion Pump:

- Draw up the volume of a vial using a sterile syringe attached to an appropriate

- needle (a vented spike or other appropriate transfer device may be used).
- Fill cetuximab into a sterile evacuated container or bag such as glass containers, polyolefin bags (e.g., Baxter Intravia), ethylene vinyl acetate bags (e.g., Baxter Clintec), DEHP plasticized PVC bags (e.g., Abbott Lifecare), or PVC bags.
 - Repeat procedure until the calculated volume has been put in to the container. Use a new needle for each vial.
 - Administer through a low protein binding 0.22-micrometer in-line filter (placed as proximal to the patient as practical).
 - Affix the infusion line and prime it with cetuximab before starting the infusion.
 - Maximum infusion rate should not exceed 5 mL/min.
 - Use 0.9% saline solution to flush line at the end of infusion.
 - The infusion rate of cetuximab must never exceed 10 mg/minute (5 mL/min). The infusion time of cetuximab should not exceed 4 hours. Patients must be continuously observed during the infusion for signs of anaphylaxis.

8.2.10 Patient Monitoring

Patients should be closely monitored for treatment-related adverse events, especially hypersensitivity reactions during the infusion and for one post-infusion observation hour. Vital signs (blood pressure, heart rate, and temperature) will be monitored and recorded prior to the administration of cetuximab, 1/2 hour into the infusion, at the completion of the infusion, and 1 hour post-infusion for the initial dose. During all subsequent administrations of cetuximab, vital signs will be monitored and recorded prior to administration of cetuximab and at the end of the infusion; however, it is recommended that the patient be observed for 1-hour post infusion.

9.0 CORRELATIVE STUDIES

9.1 Optional Tumor Biopsy

9.1.1 Collection of Specimens

Phase II patients (Arms 1 and 2 only) will be asked to consent to three optional tumor biopsies, the first at pre-treatment and the second at the end of Cycle 2 (between Days 15 and 21 inclusive) and the third at disease progression (from cetuximab and PD0332991).

Tumor tissue biopsy site will be chosen by the PI. Readily accessible sites for biopsy such as subcutaneous or dermal soft tissue masses or neck nodal masses will not likely require image guidance. In those tumor sites that are not readily accessible for biopsy such as deep neck masses or visceral organ metastases, image guidance (ultrasound or CT) will be used. The biopsy will consist of a minimum of 4 needle cores (14 gauge is preferred) or 2 small (each 4 x 4 x 4 mm) pieces of tumor. Tissue should be delivered on saline within 30 minutes of collection. Tissue

is to be stored at the Siteman Cancer Center Tissue Procurement Core Facility until analysis in the lab of [name]. The optional pre-treatment and Cycle 2 Day 15-21 and disease progression tumor biopsies (core or excisional/incisional) will be used to perform RNAseq, p16 expression, Ki-67 by IHC, total and phospho-Rb by IHC, Cyclin D1 by IHC, and TUNEL assay, and to analyze other potential biomarkers as they emerge from the scientific understanding of PD0332991 activity on formalin-fixed paraffin-embedded (FFPE) tissue.

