2.0 OBJECTIVES

2.1 Primary Objectives

1. Phase I: To determine the maximum tolerated dose of PD 0332991 when administered in combination with cetuximab to patients with incurable SCCHN

2. Phase II, Arm 1: To determine the efficacy of PD 0332991 in combination with cetuximab in incurable platin-resistant HPV-unrelated SCCHN. Efficacy will be measured by the overall response rate (ORR=CR+PR) defined by RECIST criteria.
3. Phase II, Arm 2: To determine the efficacy of PD 0332991 in combination with cetuximab in incurable cetuximab-resistant HPV-unrelated SCCHN. Efficacy will be measured by the overall response rate (ORR=CR+PR) defined by RECIST criteria.
4. Phase II, Arm 3: To determine the efficacy of PD 0332991 in combination with cetuximab in incurable cetuximab-resistant HPV-related SCCHN. Efficacy will be measured by the overall response rate (ORR=CR+PR) defined by RECIST criteria.

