Target lesions: All measurable lesions up to a maximum of 2 lesions per organ and 5 lesions in total, representative of all involved organs, should be identified as target lesions and recorded and measured at baseline. Target lesions should be selected on the basis of their size (lesions with the longest diameter), be representative of all involved organs, but in addition should be those that lend themselves to reproducible repeated measurements. It may be the case that, on occasion, the largest lesion does not lend itself to reproducible measurement in which circumstance the next largest lesion which can be measured reproducibly should be selected. A sum of the diameters (longest for non-nodal lesions, short axis for nodal lesions) for all target lesions will be calculated and reported as the baseline sum diameters. If lymph nodes are to be included in the sum, then only the short axis is added into the sum. The baseline sum diameters will be used as reference to further characterize any objective tumor regression in the measurable dimension of the disease.

Non-target lesions: All other lesions (or sites of disease) including any measurable lesions over and above the 5 target lesions should be identified as non-target lesions and should also be recorded at baseline. Measurements of these lesions are not required, but the presence, absence, or in rare cases unequivocal progression of each should be noted throughout follow-up.

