12.4 Response Criteria

12.4.1 Evaluation of Target Lesions

Complete Response (CR): Disappearance of all target lesions. Any pathological lymph nodes (whether target or non-target) must have reduction in short axis to <10 mm.

Partial Response (PR): At least a 30% decrease in the sum of the diameters of target lesions, taking as reference the baseline sum diameters.

Progressive Disease (PD): At least a 20% increase in the sum of the diameters of target lesions, taking as reference the smallest sum on study (this includes the baseline sum if that is the smallest on study). In addition to the relative increase of 20%, the sum must also demonstrate an absolute increase of at least 5 mm. (Note: the appearance of one or more new lesions is also considered progressions).

Stable Disease (SD): Neither sufficient shrinkage to qualify for PR nor sufficient increase to qualify for PD, taking as reference the smallest sum diameters while on study.

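### Arms 1 and 2: a research biopsy may excise a RECIST target lesion shortly before the first response scan, and no rule stops the removal from being scored as a partial response

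*Combined protocol and SAP*

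**What the plan says.** **Biopsies (Section 9.1.1; Arms 1 and 2, optional).** There are three: pre-treatment, "the second at the end of Cycle 2 (between Days 15 and 21 inclusive", and at progression. One sentence covers all three and gives the permitted types: "disease progression tumor biopsies (core or excisional/incisional) will be used to" perform the assays. Section 1.9 attaches the same list of types to the pre-Cycle 1 and post-Cycle 2 samples, so excision is not confined to progression. On location: "Tumor tissue biopsy site will be chosen by the PI". The sites listed as unlikely to need image guidance are "Readily accessible sites for biopsy such as subcutaneous or dermal soft tissue masses or neck nodal masses". The minimum yield is four needle cores or "2 small (each 4 x 4 x 4 mm) pieces of tumor". No maximum is given.

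**Target lesions (Section 12.2).** Targets are "All measurable lesions up to a maximum of 2 lesions per organ and 5 lesions in total". They should also suit reproducible repeat measurement. Nodes count as measurable only above 15 mm in short axis.

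**Scoring.** The primary objective in each arm (Section 2.1) reads "Efficacy will be measured by the overall response rate (ORR=CR+PR) defined by RECIST criteria". PR (Section 12.4.1) is "At least a 30% decrease in the sum of the diameters of target lesions" from baseline. CT is repeated every 8 weeks (Section 10.0), with a confirmatory scan at least 4 weeks after a first response (Section 12.1). An independent expert reviews all responses once the study is complete, ideally with patient files and images together (Section 12.4.8).

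**Decision rule (Section 15.0).** Arms 1 and 2 each enrol 30 patients and need 4 or more responders, with a table of stopping limits that starts at patient 3.

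Sections 9.1, 10.0, 12 and 15 do not bar biopsy of a target lesion, and they do not say what enters the sum of diameters once a target has been cut or removed.

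**The concern.** The lesions easiest to biopsy are often measurable ones. In a patient with no more than two measurable lesions per organ and five in total, Section 12.2 makes all of them targets. A measurable lesion chosen for biopsy in such a patient will therefore normally be a target. If it is excised in Cycle 2, the next CT shows a smaller sum of diameters for a reason unrelated to the drugs, and Section 12.4.1 read literally can call that a PR. The pre-treatment biopsy opens the same route if it follows the baseline CT, which may be up to 28 days before treatment.

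Response rate is the primary endpoint and acceptance needs only 4 responders of 30, so even one such case could matter to an arm's result.

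**Working it through.** The readable text gives no error rate or power for Arms 1 and 2, so there is no stated figure to reproduce. Three checks apply.

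**1. Timing.** Cycles last 28 days. Cycle 2 Days 15-21 are study days 28 + 15 = 43 to 28 + 21 = 49. Cycle 3 Day 1 is day 57. The gap to the first response scan is 57 − 49 = 8 to 57 − 43 = 14 days, before the ±2-day visit window.

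**2. Geometry.** With other lesions unchanged, removing d mm from a baseline sum of S mm reaches PR when d/S ≥ 0.30, that is, when S ≤ d/0.30.

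| Removed | Diameter lost (d) | PR if baseline sum is at most |
|---|---|---|
| Whole 15 mm lesion | 15 mm | 15/0.30 = 50 mm |
| Two 4 mm pieces, end to end on the measured axis | 8 mm | 8/0.30 = 26.7 mm |
| One 4 mm piece, fully on the measured axis | 4 mm | 4/0.30 = 13.3 mm |

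The last two rows are worst cases, because each piece must shorten the measured diameter by its full width. Needle cores should do little. Complete excision is the realistic route.

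**3. Effect on the decision.** Inputs from Section 15.0 are n = 30, a response rate of 13% as unacceptable, and the poor-response limits: stop at 0 responses from patient 3, at ≤1 from patient 12, at ≤2 from patient 18 and at ≤3 from patient 24 onward. An exact patient-by-patient recursion through these limits, with toxicity stopping ignored, gives:

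- No false PR, true rate 13%: P(accept) = 0.165.
- One patient certain to be scored as a PR, by position in the accrual order: 0.520 for patients 1-3, 0.259 for 4-12, 0.230 for 13-18, 0.203 for 19-24, and 0.165 (no change) for 25-30. The average over a random position is (3×0.520 + 9×0.259 + 6×0.230 + 6×0.203 + 6×0.165)/30 = 7.479/30 = 0.249.
- A false-PR probability f for each non-responder. The documents give no such rate, so f is assumed. The apparent rate is 0.13 + 0.87f:

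| Assumed f | Apparent rate | P(accept) |
|---|---|---|
| 0 | 0.130 | 0.165 |
| 1% | 0.139 | 0.191 |
| 3.3% | 0.159 | 0.253 |
| 6.7% | 0.188 | 0.343 |

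**The case against.** **Existing checks.** The independent reviewer is meant to see files as well as images, and an excision between scans should be in the file. That is a real safeguard, so it would be wrong to conclude that nothing could catch the error. But the reviewer is given no rule for such a lesion, and the review comes at study completion, after the continuous stopping decisions. The confirmatory scan does not help, because excised tissue is still absent 4 weeks later.

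**Target selection.** Section 12.2 asks for targets that can be measured reproducibly, and a lesion already marked for excision fits that poorly. This helps if the biopsy plan is known when targets are chosen. It does not cover a site chosen in Cycle 2.

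**Small samples and small nodes.** A reader might infer that any biopsy of a superficial lesion of about 10 mm threatens the endpoint. The documents do not support that. Neck nodes must exceed 15 mm in short axis to be measurable, and the specified yield is cores or small pieces, which rarely reach 30%.

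**Size.** A reader might treat the trial as a fixed sample of 30, note that exactly 3 responders at 13% has probability 0.21, and conclude that one false PR reverses about one trial in five, with P(≥4) rising from 0.559 to 0.746. Section 15.0 rules this out: an arm stops with 3 or fewer responses from patient 24 onward, so it can never finish 30 patients with exactly 3. Under the plan's own limits the rise is from 0.165 to about 0.25, and a false PR among patients 25-30 changes nothing.

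**Frequency.** Biopsies are optional and no uptake or excision rate is stated. This objection stands in full.

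**Conclusion.** The gap is real and worth closing as a low-cost improvement. If the plan is followed as written, complete excision of a target lesion in a patient with a small tumor burden can be counted as a PR on the primary endpoint in Arms 1 and 2.

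The documents do not show that this will happen or how often. The decision figures are for scale only. They rest on a true response rate of 13%, the response limits without toxicity stopping, and assumed numbers of false PRs. On that basis one false PR adds about 0.08 to the acceptance probability (0.249 − 0.165), and a 1% misclassification rate adds about 0.03 (0.191 − 0.165). Arm 3 has no research biopsies and is unaffected.

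**What to change.** Amend Sections 9.1.1 and 12.2:

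1. Take pre-treatment and on-treatment research biopsies from a non-target lesion where one is available. If only a target lesion is accessible, take needle cores only.
2. Take the pre-treatment biopsy before the baseline CT, or from a non-target lesion.
3. Record which lesion was sampled on the tumor measurement form.
4. If a target lesion is nevertheless excised or incised before progression, its reduction does not count toward PR or CR. Remove it from both the baseline and follow-up sums. If no other target remains, treat response as not evaluable. Report ORR with and without responses that depend on a biopsied lesion.

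Item 4 settles what value enters the sum. With targets of 15 mm and 35 mm, excising the first takes 50 mm to 35 mm, a 30% fall and a PR. With that lesion dropped from both sums, 35 mm to 35 mm is no change. If enrolment is already advanced, item 4 can still be fixed before the independent review.

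The cost is a few sentences in an amendment and one extra field on a form. A few patients will give only cores, or no on-treatment tissue. The progression biopsy, the sample size and the cut-off stay as they are.
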